**PROTOCOL TITLE: Efficacy of superior laryngeal nerve block for chronic cough****PRINCIPAL INVESTIGATOR: [name]****1.0 Objectives / Specific Aims**

**AIM:** Determine the overall efficacy of superior laryngeal nerve blocks for the treatment of neurogenic chronic cough. This is the primary aim of the study: to test the hypothesis that superior laryngeal nerve blocks are an effective treatment for neurogenic cough based on existing retrospective data. This will be achieved through the design of a prospective, single-blind, randomized clinical trial in which one group of patients will undergo a series of two standard (steroid-lidocaine mixture) injections and the second group will undergo a series of two placebo (saline) injections. By determining if a clinically significant difference exists between the outcomes of the two groups, measured by a dichotomous yes/no response to improvement, the Leicester Cough Questionnaire, and a visual analogue scale for symptom severity. This will provide the answer to the general question of whether or not these injections are clinically effective for patients with neurogenic cough. Furthermore, any adverse reactions will be thoroughly documented. The significance of this specific aim is to confirm the clinical utility of superior laryngeal nerve blocks; if proven effective, this can greatly improve the care of these patients by allowing for an evidence-based treatment option.

Given the focus and timeframe of the proposed project, this one aim to determine overall efficacy is sufficient; however, it could be further subdivided:

**Aim 1a:** Determine if patients who undergo a series of superior laryngeal nerve blocks report improvement in cough severity and quality of life.

**Aim 1b:** Determine the placebo effect of superior laryngeal nerve blocks in the treatment of neurogenic chronic cough.

**Aim 1c:** Determine the average amount of time post-injection at which symptoms return.

**Aim 1d:** Determine the rate of complications of in-office superior laryngeal nerve blocks.

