Recently, we retrospectively reviewed our experience at the Medical University of South Carolina with in-office SLN blocks for the treatment of chronic neurogenic cough and our unpublished data are consistent with the work of Simpson, et al. and Dhillon. We found that within a cohort of 23 patients (4 males, 19 females, average age 63.6 years), 17 (74%) reported improvement with the injections, 2 (9%) reported initial improvement followed by return to baseline, and 4 (17%) did not have any improvement. The average number of SLN blocks performed per patient was 3.8. Of the 23 patients, 13 had recorded pre- and post-treatment Hull Cough Sensitivity Questionnaire scores and changes in scores were significantly improved from an average of 38 to 23 ( $p = 0.005$ ). All patients reported their symptom severity on a scale of 0-10 and there was a significant negative correlation between the number of injections and symptom severity scores with the largest difference following the initial injection (Figure 1). There were no major adverse events, however 4 patients (17%) reported self-limited post-injection globus sensation.

Although the current data support the efficacy and safety of SLN blocks for chronic neurogenic cough, there are no prospective investigations. Questions remain regarding safety and efficacy, particularly the potential for placebo effect, as well as proper medication dosing and timing. Our hypothesis is that superior laryngeal nerve blocks will provide significant improvement in cough severity compared to placebo. By better understanding the efficacy of superior laryngeal nerve blocks in the treatment of chronic cough, the care of patients presenting with this common symptom will be optimized.

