## **6.0 Number of Subjects**

We will recruit 50 patients. Our institution has several otolaryngologists who routinely treat chronic cough and, within the past year, a single provider performed superior laryngeal nerve blocks on 29 patients, with the majority of the injections occurring within the last 2-3 months. Therefore, we are confident in our ability to recruit 50 patients within 1 year. Assuming a dichotomous outcome of >50% improvement or not, a 70% treatment effect, a 25% possible incidence of improvement in placebo, and an 80% confidence level, we would need 18 patients in each group (total N=36) to power our study.

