### **Figure 2. Flow Diagram of Study Design**

Injection will be completed near the lateral thyrohyoid membrane by a single experienced laryngologist per previously published methodology utilizing bony, soft tissue and cartilaginous landmarks. An illustration of the anatomic target for the injection can be seen in Figure 3. To minimize patient discomfort, lidocaine cream will be applied to the skin prior to injections.

Following injection, patients will be instructed to follow up in a 2- to 3-week time frame; however, we will include all patients in analysis if they follow up within 1-4 weeks. Any follow up outside of that window will lead to removal of the patient's data from the analysis. At follow up, if the patient's cough has improved by greater than or equal to 50% compared to baseline, we will repeat the injection on the same side. If less than 50%, we will move to the other side to perform the injection. Patients will undergo a total of two injections before data collection is complete for analysis. If patients were to experience full resolution of cough (i.e. report 0/10 for cough severity) after the first injection alone, then at that point, their condition would be considered cured and their enrollment in the study will finish. The reason for this is to avoid unnecessary and unindicated injections in patients with resolution of cough.

2 weeks after the second injection, participants will be unblinded. If in the placebo group, they will have the opportunity to complete 2 additional treatment injections (unblinded) under the study protocol. Data will be collected and stored in the same fashion as prior to unblinding.

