**Figure 3. Anatomic Target of Superior Laryngeal Nerve Blocks.**

During the procedure, the thyroid cartilage, hyoid, and thyrohyoid membrane are palpated as key anatomic landmarks. The target of the injection, the superior laryngeal nerve, pierces the thyrohyoid membrane superior to the superior laryngeal artery. The plunger is drawn back prior to injection to ensure needle tip is not intravascular. Illustration by author.

Patients will be provided a log to track their progress throughout treatment. This will include a visual analogue scale to be completed daily after each injection to document cough severity, as well as opportunities to document any adverse effects or general comments. An example of this log can be seen in Figure 4. At each follow up visit, patients will provide a dichotomous answer (Yes or No) if they experienced improvement in cough and will disclose how long the improvement lasted. They will also fill out the Leicester Cough Questionnaire (LCQ), a validated 19-question quality of life survey for chronic cough. The LCQ will be the study's primary outcome measure. Please see Appendix 1 for a copy of the Leicester Cough Questionnaire. After the last injection, patients will return to the clinic in three months or opt to be contacted via telephone to assess if symptoms have returned.

Date of last injection: _____
 
WEEK 1  Please mark on the line below with a "X" how severe you believe your cough is. The far left indicates no cough at all, and the far right is indicative of the most severe cough.
 
Day 1 no cough ..... severe cough
 
Day 2 no cough ..... severe cough
 
Day 3 no cough ..... severe cough
 
Day 4 no cough ..... severe cough
 
Day 5 no cough ..... severe cough
 
Day 6 no cough ..... severe cough
 
Day 7 no cough ..... severe cough
	

Date of last injection: _____
 
WEEK 2  Please mark on the line below with a "X" how severe you believe your cough is. The far left indicates no cough at all, and the far right is indicative of the most severe cough.
 
Day 1 no cough ..... severe cough
 
Day 2 no cough ..... severe cough
 
Day 3 no cough ..... severe cough
 
Day 4 no cough ..... severe cough
 
Day 5 no cough ..... severe cough
 
Day 6 no cough ..... severe cough
 
Day 7 no cough ..... severe cough
	

Any side effects?
	
Any side effects?

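### The three-month contact asks whether symptoms have returned without tying this to earlier improvement or a reference level, and no graded measure is provided by telephone

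*Combined protocol and SAP*

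**What the plan says.** Section 1.0, Aim 1c, is to "Determine the average amount of time post-injection at which symptoms return". Two sources could inform it.

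- **Follow-up visits (Section 10.0).** Visits count if they fall 1 to 4 weeks after an injection. At each one the patient says whether the cough improved, says for how long, and completes the LCQ. A daily visual analogue log is also kept after each injection; the example log covers two weeks.
- **Three-month contact (Section 10.0, text below Figure 3).** The text reads: "After the last injection, patients will return to the clinic in three months or opt to be contacted via telephone to assess if symptoms have" (ending 'returned'). No restriction to improvers, reference level or threshold is given.

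Three other statements bear on this contact.

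- A patient who reports 0/10 after the first injection leaves early: "their condition would be considered cured and their enrollment in the study will finish".
- Two weeks after the second injection patients are unblinded, and placebo patients may take two open-label active injections.
- Section 17.0 treats the contact as a three-month follow-up.

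Section 12.0 gives no analysis for the three-month answer or for Aim 1c.

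**The concern.** Whether symptoms have come back is clear only for a patient whose cough went away.

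- **Never improved.** The cough did not leave, so it cannot return. A literal no puts this patient beside those with lasting benefit. A yes records a relapse that did not happen.
- **Partly improved,** for example from 8/10 to 4/10. Symptoms are present throughout, so either answer is defensible and loss of benefit is not captured.
- **Fully resolved after one injection.** The question fits this patient best, but enrolment has ended and the plan does not say whether the contact is made.

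Any statement on how long benefit lasts is at stake. The visit data cannot replace the three-month answer, because a duration reported at 1 to 4 weeks is cut off at that visit for anyone still improved. If the contact yields only an ambiguous yes or no, better information cannot be recovered later.

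**Working it through.** **Step 1. Reading the planning figures.** Section 6.0 starts from this: "Assuming a dichotomous outcome of >50% improvement or not". It then gives "a 70% treatment effect, a 25% possible incidence of improvement in placebo, and an 80% confidence level, we would need 18 patients in each group". I take 70% and 25% as response rates and the 80% as power. A two-sided alpha of 0.05 is assumed, as none is stated.

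n = [1.960 × √(2 × 0.475 × 0.525) + 0.842 × √(0.70 × 0.30 + 0.25 × 0.75)]² / (0.70 − 0.25)² = (1.384 + 0.531)² / 0.2025 ≈ 18.1 per group.

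This rounds up to 19 against the stated 18. Power at 18 per group is 79.8%. Reading 70% as an absolute difference (95% v 25%) gives 7 per group, so the response-rate reading fits the plan's figure.

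**Step 2. Patients without the planning response.** Section 10.0 allocates 25 per arm.

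- Treatment: 25 × 0.30 = 7.5
- Placebo: 25 × 0.75 = 18.75
- Total: 26.25 of 50 = 52.5%

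**Step 3. Range.** Uptake of the open-label injections is not stated. A 70% response to them is assumed.

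| Assumption | Without >50% response | Share of 50 |
|---|---|---|
| No crossover | 7.5 + 18.75 = 26.25 | 52.5% |
| Half of placebo cross over | 7.5 + 12.5 × 0.75 + 12.5 × 0.30 = 20.6 | 41% |
| All of placebo cross over | 7.5 + 25 × 0.30 = 15.0 | 30% |
| All placebo non-responders, and only they, cross over | 7.5 + 18.75 × 0.30 = 13.1 | 26% |
| 70% read as a difference, no crossover | 25 × 0.05 + 18.75 = 20.0 | 40% |
| Site's 4 of 23 with no improvement used for treatment, no crossover | 25 × 4/23 + 18.75 = 23.1 | 46% |

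**Step 4. How far an unstated coding rule could move the answer.** This is an illustration only. Assume no crossover, non-responders treated as non-improvers, and the same relapse proportion r among responders in both arms, so that durability does not truly differ. Scoring non-improvers as not returned gives 0.70r v 0.25r. Scoring them as returned gives 0.30 + 0.70r v 0.75 + 0.25r.

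| r | Scored not returned, active v placebo | Scored returned, active v placebo |
|---|---|---|
| 25% | 17.5% v 6.25% | 47.5% v 81.25% |
| 50% | 35% v 12.5% | 65% v 87.5% |
| 75% | 52.5% v 18.75% | 82.5% v 93.75% |

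The apparent direction reverses with the coding at every r shown.

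**The case against.** A reader might infer that the item miscounts about half the trial. The documents do not support that, for these reasons.

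- **No three-month analysis is stated,** so nothing is yet counted wrongly. The pairs in Step 4 come from coding rules and relapse rates that I supplied. They do not show that the trial would favour placebo.
- **The 52.5% is not a count of patients who never improved, or of those who never improved or improved only partly.** It counts patients without more than 50% improvement. Someone with 40% improvement is inside it and has benefit to lose. Someone with 60% is outside it and is still a partial improver. The documents' only never-improved figure is 4 of 23 (17%), in treated patients.
- **Never-improvers can already be identified** from the yes/no answers at visits.
- **A partial improver can have a valid value.** The site's own cohort includes 2 of 23 who improved and then went back to baseline.
- **Clinic attenders may already complete the LCQ** if the three-month contact counts as a follow-up visit, as Section 17.0 suggests.
- **Group means do not show that partial improvement is the typical individual result.** Section 2.0 reports that "changes in scores were significantly improved from an average of 38 to 23" (23/38 = 61% remaining, 13 of 23 patients), and a published series fell from 26.8 to 14.6 (54% remaining). A mix of strong responders and non-responders could give the same means.
- **Durability is not an endpoint in Section 4.0,** and Section 1.0 offers Aim 1c as an optional subdivision of a single aim.

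All of this stands, and it limits the size and weight of the point. None of it supplies a reference level, a rule on who can have a return, or a graded measure by telephone. If the LCQ is taken in clinic only, the measurement differs by contact mode, which the patient chooses.

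**Conclusion.** The point holds as a measurement weakness in the only planned source on durability beyond the 1-to-4-week visits. The question is put to all patients, does not fit never-improvers, is ambiguous for partial improvers, and may be backed by the LCQ in clinic but not by telephone.

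Up to about half of patients (26.25 of 50) may lack the more-than-50% response used in planning. That rests on the Section 6.0 rates, 25 per arm and no crossover. With high crossover uptake and an assumed 70% response, the share falls to about 26% to 30%.

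The primary LCQ comparison is unaffected. The change is worth making before the contacts begin, because it is cheap and the data cannot be collected afterwards.

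**What to change.** **Section 10.0, three-month contact.** Replace the question on return of symptoms with three items, asked identically in clinic and by telephone:

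- the LCQ;
- a 0-10 cough severity rating;
- 'Compared with before your first injection, is your cough still improved (yes/no)?'

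Repeat the existing visit question on how long improvement lasted, so that a time is available when the answer is no. Record the LCQ and the 0-10 rating before the first injection as the reference; the change-score analysis in Section 12.0 already implies this for the LCQ.

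**Section 12.0.**

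- Report 'still improved' descriptively by arm, with never-improved patients counted as not improved.
- Report time to return only among patients who had reported improvement. Define return as loss of that improvement relative to the pre-injection score, and show the number still improved beside it.
- Report placebo patients who took open-label injections as a separate group, described as following active injections.
- Make no randomised between-arm durability claim at three months.

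**Section 10.0, early exit.** Reconcile the statement that enrolment ends at 0/10 with the three-month contact, so that it is clear whether these patients are contacted.

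**Cost.** Protocol wording, a 19-item questionnaire and a few short questions at a contact already planned, with no extra visit or patients. Each contact takes a few minutes longer, and the durability figure will look less favourable because never-improvers stay in the denominator.

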**Figure 4. Patient Symptom Log**

**11.0 Specimen Collection and Banking (if applicable)**  
 Not applicable.

## 12.0 Data Management

Descriptional analysis of all demographic data, including sex and age, will be completed. Dichotomous data will be summarized as percentages per group per injection and compared via chi-squared analysis. Changes in Leicester Cough Questionnaire scores, both global and specific domains (physical, psychological and social), will be analyzed via a linear regression model. An independent t-test will then be used to compare both study arms. Regression analysis will also be performed on the data collected from the patient log, specifically the daily visual analogue scale. A ruler will be used to the identify the exact percentage along the scale that represents the patient's cough severity. A comprehensive compilation of side effects reported by the treatment group will be reported as a proportion of the total number of patients in the treatment study arm (n = 25) and compared to the placebo group (n=25). The data collected from the placebo group pre-unblinding will be directly compared to the results achieved from treatment injections offered following unblinding.

Data will not leave MUSC. Patient identifiers (MRN) will be kept coded on a separate, password-protected file stored on a secure drive.

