#### 4.0 Study Endpoints (if applicable)

Primary study endpoints include improvement in cough, measured by dichotomous yes/no response to improvement, the Leicester Cough Questionnaire (LCQ), and a visual analogue scale for symptom severity. Due to its validation, the LCQ will be the primary outcome measure. Secondary study endpoints include the complication and side effect rate from the injections.

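### The implied primary analysis, a t-test on change in LCQ, is valid, but adjusting for baseline LCQ is usually more precise, and the primary visit should be named with a rule for patients who finish after injection 1

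*Combined protocol and SAP*

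**What the plan says.** Section 4.0 lists three measures of improvement and then singles one out: "Due to its validation, the LCQ will be the primary outcome measure". Section 10.0 repeats this and has the LCQ completed at each follow-up visit, so it exists after injection 1 and after injection 2.

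Section 12.0 gives the LCQ analysis in two consecutive sentences: "Changes in Leicester Cough Questionnaire scores, both global and specific domains (physical, psychological and social), will be analyzed via a linear regression model", and then "An independent t-test will then be used to compare both study arms". The regression's covariates are not stated. For the yes/no outcome the same section fixes the occasions ("Dichotomous data will be summarized as percentages per group per injection"); for the LCQ it gives none.

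Three statements in Section 10.0, in the text under Figure 2, bear on the visit:

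- Data collection for analysis is complete after two injections.
- For a patient with full resolution after the first injection, "their condition would be considered cured and their enrollment in the study will finish".
- On timing, "we will include all patients in analysis if they follow up within 1-4 weeks", while "2 weeks after the second injection, participants will be unblinded".

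**The concern.** Two things are at stake.

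**Precision.** The trial has at most 50 patients, and fewer once out-of-window follow-up is removed. A change score subtracts the whole baseline value. A regression estimates how much of it to subtract, and that usually leaves less residual variance. The baseline LCQ is needed in any case, because the plan analyses changes.

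**A uniquely defined primary result.** The visit after injection 2 can be inferred but is not named. On that inference, patients whose cough resolved fully after injection 1 have no primary value. Whether a patient has an outcome then depends on response, and the best responders are the ones left out. If the visit is settled only after the data are seen, the nominal 5% error rate is no longer assured.

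**Working it through.** **Inputs from the documents.** 25 per arm (Sections 10.0 and 12.0); LCQ at two follow-up visits (Section 10.0); t-test on change (Section 12.0).

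**Assumed, because the documents give no LCQ SD or correlation.** Correlation ρ of baseline with follow-up LCQ 0.3 to 0.8; ratio k of follow-up SD to baseline SD 0.8, 1 or 1.25; correlation between the two follow-up LCQs 0.6 or 0.8; two-sided 5% level.

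**The plan's own figure.** Section 6.0 states 18 per group for 70% versus 25% on a dichotomous outcome. Reading the stated 80% as power, the arcsine formula gives 17.95, rounded up to 18; the pooled two-proportion formula gives 19. The figure reproduces, but it says nothing about LCQ precision.

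**Step 1: precision.** With baseline SD set to 1:

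- Var(change) ∝ 1 + k² − 2ρk
- Var(adjusted) ∝ k²(1 − ρ²)
- The difference is (1 − ρk)², which is never negative. Apart from the cost of estimating the slope, adjustment cannot lose.

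Example, k = 1 and ρ = 0.5: 1 + 1 − 1 = 1.00 against 1 − 0.25 = 0.75. The ratio is 0.75, so the SE falls by 1 − √0.75 = 13%.

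| k | ρ = 0.3 | 0.5 | 0.7 | 0.8 |
|---|---|---|---|---|
| 0.8, variance ratio | 0.502 | 0.571 | 0.628 | 0.640 |
| 0.8, SE reduction | 29% | 24% | 21% | 20% |
| 1, variance ratio | 0.650 | 0.750 | 0.850 | 0.900 |
| 1, SE reduction | 19% | 13% | 8% | 5% |
| 1.25, variance ratio | 0.784 | 0.893 | 0.981 | 1.000 |
| 1.25, SE reduction | 11% | 5.5% | 1% | 0% |

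Estimating the slope multiplies the adjusted variance by about 1 + 1/(N − 4) = 1 + 1/46 = 1.02 at N = 50. The worst case shown (k = 1.25, ρ = 0.8) therefore loses about 2% of variance. With equal SDs the SE reductions become 18.5/12.5/6.8/4.1%.

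In terms of power, take an assumed difference of 0.8 SD, equal SDs and 25 per arm. The t-test on change has 67/81/96% power at ρ = 0.3/0.5/0.7; the adjusted model has 84/90/98%.

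**Step 2: validity and choice of visit.** Simulation with normal data, no treatment effect, 25 per arm, over the grid above:

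| What is done | Type I error |
|---|---|
| t-test on change at one fixed visit | 4.8–5.3% |
| t-test, better of the two visits taken afterwards | about 7–10% |
| t-test or adjusted model at one visit, smaller p taken | 5.6–8.3% |
| Either analysis at either visit, smallest p taken | 9.8–14.7% |

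The first row shows that the planned test is valid. The second is the case closest to the text. The last two apply only if a baseline-adjusted model is also an option, and the plan never mentions one. If the plan's regression holds arm only, it reproduces the pooled t-test and adds nothing. All rows assume that every patient has both LCQs, which Section 10.0 contradicts for patients who resolve after injection 1.

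**Step 3: early finishers.** Set the end of data collection after two injections beside the early-finish rule. A patient with full resolution after injection 1 has a first follow-up LCQ and no second. No sentence says whether the first one counts.

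**The case against.** The plan can be read as more definite than this point suggests, and much of that reading stands. The t-test is the only method that Section 12.0 ties to the arms, and the word linking the two sentences suggests a sequence rather than rival analyses. The regression may be descriptive. Section 10.0 also points to the visit after injection 2. A reader might infer that the plan has no primary analysis at all, or that its error rate runs to 15%. The documents do not support either: a test and a visit are implied, and the figure near 15% needs a model that the plan does not contain.

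It is also fair to say that baseline adjustment is an improvement and not a correction. The t-test on change already uses baseline and is unbiased under randomisation. If a mixture of responders and non-responders widens the follow-up scores, the gain may be small or nil.

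Finally, a reader might infer that primary LCQs will be completed after unblinding. Section 10.0 does not say so. That could happen only if the 1–4 week window also applies after injection 2 and the participant is told the arm before completing the questionnaire. Disclosure at the visit, after the LCQ, is equally compatible with the text.

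What these arguments leave standing is the better use of the baseline LCQ, the undesignated visit, and the missing rule for patients who finish early.

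**Conclusion.** The point holds as a low-cost improvement with one real gap. The t-test on change in LCQ is the implied arm comparison and is valid. A regression on arm and baseline LCQ would usually be more precise, by 0–29% of the SE over the assumed range and by 5–19% with equal SDs, with about 2% of variance at risk. These sizes rest wholly on assumed correlations and SD ratios.

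The gap is the primary assessment: it is implied, not named, and on the implied reading it leaves out patients with full resolution after injection 1. The type I error of about 7–10% is what choosing the visit after seeing the data would cost. It is not a claim that this will happen.

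**What to change.** Replace the two LCQ sentences in Section 12.0 with:

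> The primary analysis is a linear regression of total LCQ at the primary assessment on treatment arm and total LCQ before injection 1; the arm coefficient with its 95% CI is the primary result. The primary assessment is the LCQ at the follow-up visit after the second injection or, for patients whose participation ends after the first injection because of full resolution, the LCQ at that visit. Domain scores use the same model as secondary analyses; a t-test on change is supportive only.

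In addition:

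- Report how many patients in each arm contribute a first-visit LCQ, and repeat the model on the first follow-up LCQ for all patients as a sensitivity analysis.
- State how LCQs that are missing for other reasons, or out of window, are handled, and whether the removal rule in Section 10.0 applies to this model.
- Confirm that the baseline LCQ is recorded before injection 1. It is implied by the analysis of changes but not stated.
- Reconcile in Section 10.0 the unblinding time with the follow-up window, so that the LCQ after the second injection is completed before the participant is told the arm.

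The cost is wording, plus settling the order of LCQ and unblinding; no extra patients are needed. The main downside is that the primary assessment mixes LCQs after one and two injections and may credit a resolution that does not last. In the retrospective series in Section 2.0, 2 of 23 patients (9%) improved and then returned to baseline. The first-visit sensitivity analysis would show how much the mixing matters; it would not remove it.

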## **10.0 Study Design / Methods**

Figure 2 depicts the flow diagram of the study design. Once patients have met inclusion and exclusion criteria (including undergoing all diagnostic testing for other potential causes of chronic cough) and have agreed to study participation, informed consent will be obtained and they will be randomized into two groups: treatment and placebo. This will be achieved using randomly-assorted, secured envelopes containing a card indicating whether the patient will be in the treatment or placebo group. This will be unveiled immediately to the provider administering the first injection, but remain unknown to the subject. There will be 25 "Treatment" and 25 "Placebo" cards within the 50, individually-secured envelopes. On initial visit, prior to the injection, patients will first undergo nasal laryngoscopy as part of standard of care. If there is any vocal fold weakness seen on scope examination or if there is a unilateral trigger point identified, then the first injection will start on the side of the suspected neuropathy. If there is no evidence of neuropathy on examination, we will start with a left-sided injection. Injections will be standardized to 2 mL of a 1:1 triamcinolone 40mg: 1% lidocaine with 1:200,000 epinephrine. Injection syringe will be brought into room by the physician in an opaque box and placed behind patient so they cannot view the syringe prior to injection. During the injection, a paper "shield" will be held under the patient's chin by an assistant and they will be asked to close their eyes so that they are not able to view the syringe during injection. This is necessary as steroid possesses a white color as compared to clear saline. The practitioner is not blinded so that proper drawing back on the syringe is not compromised to avoid intravascular or airway injection.

[figure not shown]

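### The side-effect rate in Section 12.0 counts only the 25 patients randomised to treatment, so it leaves out active injections given to placebo patients after unblinding, although Aim 1d concerns the blocks themselves

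*Combined protocol and SAP*

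**What the plan says.** Section 1.0 sets Aim 1d: "Determine the rate of complications of in-office superior laryngeal nerve blocks". Section 4.0 makes the complication and side-effect rate of the injections the secondary endpoint. Both refer to the procedure, not to one randomised arm.

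Section 12.0 gives the only rule for the rate. It begins "A comprehensive compilation of side effects reported by the treatment group will be reported" and sets the denominator and comparator as a "proportion of the total number of patients in the treatment study arm (n = 25) and compared to the placebo group (n=25"). Its next sentence plans a comparison, within the placebo group, of data from before unblinding with results of the active injections offered afterwards. It does not name side effects.

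Section 10.0 (text after Figure 2) unblinds participants two weeks after the second injection and offers placebo patients two active injections within the protocol. Of that phase it says: "Data will be collected and stored in the same fashion as prior to unblinding". The patient log (Figure 4) has a field for side effects. The same section says of visits outside 1 to 4 weeks: "Any follow up outside of that window will lead to removal" of the patient's data from the analysis. It makes no exception for safety data.

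**The concern.** The quantity wanted is the complication rate of the block. Every patient who receives an active injection under the protocol, with side effects logged, informs it. The stated rule uses only those randomised to active drug. Up to 25 further exposed patients contribute to no planned complication rate, in a trial whose background section says that safety questions remain open.

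Two gaps in the wording add to this. The placebo side-effect proportion has no stated end point, although the same patients may later receive active drug. The denominator is also written as a fixed 25 per arm, while Section 10.0 can remove a patient's data, Section 10.0 lets enrolment end after one injection, and Section 13.0 allows withdrawal. At stake are the precision of the safety estimate and a clear definition of the arm comparison.

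**Working it through.** **The plan's own figure.** Section 6.0 states "We will recruit 50 patients". Section 10.0 allocates them by 25 treatment and 25 placebo envelopes, so 50 / 2 = 25 per arm. The denominators in Section 12.0 are the planned allocation and reproduce exactly.

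**Active exposure left out.** Inputs: 25 patients per arm; two injections each in the randomised period (Section 10.0); up to two open-label active injections per placebo patient (Section 10.0). Uptake is not given, so the number crossing over, x, is taken from 0 to 25. All counts assume two injections per patient. They are maxima, because a patient whose cough resolves fully after the first injection stops there.

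- Patients given active drug = 25 + x
- Active injections = 2 × 25 + 2x
- Share outside the stated rule = 2x / (50 + 2x)
- Upper limit with zero events (one-sided 95%) = 1 − 0.05^(1/n), n = 25 + x

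| Crossing over (x) | Patients given active drug | Active injections | Share left out | Zero-event upper limit |
|---|---|---|---|---|
| 0 | 25 | 50 | 0/50 = 0% | 1 − 0.05^(1/25) = 11.3% |
| 12 (about half) | 37 | 74 | 24/74 = 32% | 1 − 0.05^(1/37) = 7.8% |
| 25 (all) | 50 | 100 | 50/100 = 50% | 1 − 0.05^(1/50) = 5.8% |

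The limit for the stated rule is the first row whatever the uptake, since its n stays at 25.

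**A commoner event.** Section 2.0 reports self-limited globus in 4 of 23 patients (17%) in the site's own series. At an illustrative 16%, the exact (Clopper-Pearson) 95% interval is 4.5% to 36.1% for 4/25 and 7.2% to 29.1% for 8/50. The second interval assumes full crossover and the same event rate in both periods. The site's patients averaged 3.8 blocks, not two, so this shows scale and is not a forecast.

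**If the placebo count did not stop at unblinding.** Take p1 = 4/23 = 17.4% as the active rate, assume a saline rate p0, let c be the uptake, and assume independence. The placebo-arm proportion is then 1 − (1 − p0)(1 − c × p1).

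- p0 = 0%: 0% counted to unblinding; 17.4% with later events at full uptake
- p0 = 5%: 5.0%; 1 − 0.95 × 0.826 = 21.5%
- p0 = 10%: 10.0%; 25.7%

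**If removal applied to side effects but n stayed at 25.** Suppose, as an assumption, that 5 of 25 treated patients were removed. A true 17.4% would appear as 17.4% × 20/25 = 13.9%.

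The last two calculations show why the wording should be settled. They are not predictions of what the analysis will do.

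**The case against.** The strongest reply is that the plan already separates the two periods. The sentence after the denominators sets placebo data from before unblinding against open-label results, and Section 10.0 says "Patients will undergo a total of two injections before data collection is complete for analysis". The natural reading is that the placebo group of 25 means the saline period. A reader might infer that active-drug events will be counted as placebo events and dilute the comparison. The documents do not support that: it is a possible reading, but the plan's own split works against it. What stands is that no sentence states the cut-off for side effects, and that the within-placebo comparison, even if it covers them, gives no rate over all active exposure.

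A reader might also infer that removed patients' events will drop out of the numerator while 25 remains below the line. That is not established either. A planned n in a protocol is ordinary, Section 1.0 promises thorough documentation of adverse reactions, and Section 13.0 has the logs reviewed at least every four weeks. The removal wording is nevertheless broad enough to cover safety data, so an explicit exemption is warranted.

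Full crossover is a ceiling. The offer is optional, the plan itself expects 25% improvement on placebo (Section 6.0), and patients may withdraw or finish early. The result must therefore be given as a range.

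Finally, this is a secondary endpoint, the comparison of arms before unblinding is valid, and the data are collected anyway, so a fuller table could be made at reporting. Participant protection does not depend on the denominator: Sections 13.0 and 15.0 do not limit the handling of serious events by arm. All of this stands, and it lowers the priority.

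**Conclusion.** The point holds as a matter of precision and definition. Section 12.0 answers Aim 1d from the treatment arm alone and leaves out between 0% and 50% of active injections, depending on an uptake that the documents do not give; at about half uptake the share is 32%. The corresponding zero-event upper limits are 11.3% with 25 exposed patients, 7.8% with 37 and 5.8% with 50. These figures assume two injections per patient, full enrolment and, for the pooled limits, the same risk in the randomised and open-label periods.

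The end of the placebo count and the treatment of safety data under the removal rule are unstated. Bias from either is a risk of the wording, not a demonstrated effect. The efficacy analysis and sample size are untouched. This is a cheap improvement of low to moderate priority.

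**What to change.** In Section 12.0:

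1. Keep the randomised side-effect comparison. State that in both arms it covers the period before unblinding, and so before any open-label injection. Count events among, and divide by, all patients actually injected in each arm, including those with out-of-window visits, in place of a fixed 25. Say that the removal rule in Section 10.0 does not apply to safety data.
2. For Aim 1d, add a complication rate over all patients who received any active injection, with exact 95% intervals per patient and the randomised and open-label sources shown separately as well as together. If a per-injection rate is also given, use an interval that allows for repeated injections in one patient (for example, a patient-level bootstrap or a cluster-robust interval). A plain binomial interval over injections would generally be too narrow.

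The cost is a few sentences and one extra table from data already being collected. The drawback is that open-label reports are unblinded and come from patients who have already had saline injections, so the two sources may differ. Showing them separately lets the reader judge that.
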